14.4 Pregnancy

Women of childbearing potential (WOCBP) include any female who has experienced menarche and who has not undergone successful surgical sterilization (hysterectomy, bilateral tubal ligation or bilateral ovariectomy) or is not postmenopausal (defined as amenorrhea >12 consecutive months and for women on hormone replacement therapy, only with a documented plasma follicle stimulating hormone level greater than 35 mIU/mL). In cases where a woman's partner is sterile (e.g., vasectomy), she is considered to be of childbearing potential. Even women who are using oral, implanted or, injectable contraceptive hormones, an intrauterine device (IUD), barrier methods (diaphragm and spermicidal, condom and spermicidal) to prevent pregnancy, or practicing abstinence should be considered to be of childbearing potential. Post-menopausal women who have fertilized eggs implanted are considered to be of childbearing potential.

All WOCBP participating in the clinical trial must use appropriate method of birth control or continuous abstinence from heterosexual sexual contact during the course of the clinical trial until the *onset of the first menses after the last dose of trial medication*, in a manner such that risk of failure is minimized

Any of the following methods of birth control are acceptable: oral contraceptives, contraceptive patches/implants, Depo-Provera®, double barrier methods (e.g., condom and spermicide) or IUD. Female subjects must have a negative urine pregnancy test at baseline.

Prior to clinical trial enrollment, all WOCBP must be advised of the importance of avoiding pregnancy during clinical trial participation and the potential risk factors for an unintentional pregnancy. The subject must sign an informed consent form (ICF) documenting this discussion.

WOCBP should be instructed to contact the investigator immediately if they suspect they might be pregnant (e.g., missed or late menstrual period). The test article must immediately be withheld if it can be done safely until the result of pregnancy testing having a minimum sensitivity of at least 25 mIU/mL for hCG is known. If pregnancy is confirmed, the test article must be permanently discontinued if this can be done safely and in an appropriate manner (e.g., dose tapering if necessary for subject safety) and the subject must be withdrawn from the clinical trial. Exceptions to clinical trial discontinuation may be considered for life-threatening conditions only after consultation with the Medical Monitor. The investigator must follow the subject to determine the outcome and follow up the neonate for 8 weeks post -delivery to know the outcome and health status of the neonate.

Sponsor Name: Actavis, LLC Protocol: 094-3153-301, v1.0

Protocol-required procedures for clinical trial discontinuation and follow-up must be performed unless contraindicated by pregnancy (e.g., x-ray studies). Appropriate pregnancy follow-up procedures should be considered if indicated.

14.4.1 Reporting Procedure

The investigator must report any pregnancy associated with exposure to test article within 24 hours of becoming aware of the pregnancy using the appropriate pregnancy surveillance form(s) to the Medical Monitor or Project Manager listed on page 1 of the protocol. If pregnancy was associated with an AE, procedures for AE reporting should be followed. If pregnancy was associated with a SAE, procedures for SAE reporting must be followed. Spontaneous abortion is always considered a serious adverse event. The investigator must report information regarding the course of the pregnancy, including perinatal and neonatal outcome on the pregnancy surveillance form(s). The investigator must notify the IRB of any pregnancy associated with the study therapy and keep careful source documentation of the event.

15. BLINDING/UNBLINDING

This is a double-blind, randomized, vehicle-controlled study. Blinding is important for the integrity of this clinical drug trial. However, the blind may be broken in the event of a medical emergency in a subject, in which knowledge of the test article identity is critical to the subject's management. Before breaking the blind for a subject, the investigator should determine that the information is necessary (i.e., that it will alter the subject's immediate management). In many cases, particularly when the emergency is clearly not test article related, the problem may be effectively managed by assuming that the subject is receiving active product without the need for unblinding. If possible, before breaking the blind, contact the responsible Medical Monitor.

16. CLINICAL SUPPLIES

16.1 Test Article Information

Test articles will be packaged and labeled by the Sponsor or designee. Detailed information on the packaging/labeling, blinding/unblinding, storage and preparation, dispensing, accountability etc. is included in **Appendix 2**.

16.2 Additional Supplies Provided by

will provide the following additional supplies to the study sites:

- Case report forms.
- Site Regulatory Binder or document filing system.
- Urine pregnancy test kits.

Sponsor Name: Actavis, LLC Protocol: 094-3153-301, v1.0

• Large plastic bags for subjects to transport study drugs, diary and instruction sheet.

• Miscellaneous supplies such as markers for AK counting.

16.3 Supplies Provided by Investigator

• Urine collection containers.

16.4 Supplies Provided by Actavis, LLC

• Pumps containing vehicle cream for demonstration to subjects of test article application.

17. STATISTICAL CONSIDERATIONS

17.1 Sample Size

ioequivalence was concluded if the 90% continuity-corrected confidence interval on the difference in active treatment complete clearance rates was between -0.20 and +0.20 in the per protocol (PP) population, and each active treatment was found to be statistically superior to the vehicle by independent continuity-corrected Z-tests in the intent-to-treat (ITT) population.

total of 435 ITT subjects
for demonstrating superiority of each active treatment over the vehicle treatment.

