I understand the study may be terminated or enrollment suspended at any time by Actavis, LLC, with or without cause, or by me if it becomes necessary to protect the interests of the study subjects.

Any additional information added to this protocol is also confidential and proprietary to Actavis, LLC and must be treated in the same manner as the contents of this protocol.

Printed Name of Principal Investigator	
Investigator Signature	Date
Protocol number: 094-3153-301	Site number:
Version: 1.0	

DATE OF FINAL VERSION: July 30, 2013

Sponsor Name: Actavis, LLC Protocol: 094-3153-301, v1.0

PROTOCOL SYNOPSIS

Title	A Multicenter, Randomized, Double-Blind, Vehicle-Controlled, Parallel Group Comparison Study to Determine the Therapeutic Equivalence of Generic Imiquimod Cream, 2.5% and Zyclara® (imiquimod) Cream, 2.5% in Subjects with Actinic Keratoses			
Study Type	Bioequivalence with Clinical Endpoint			
Test Articles	 Imiquimod cream, 2.5% (Actavis) (generic imiquimod) Zyclara® (imiquimod) Cream, 2.5% (Medicis) (Reference Listed Drug) Vehicle cream (Actavis) 			
Study Objective	To evaluate the safety and therapeutic equivalence of generic imiquimod cream, 2.5% to Zyclara (imiquimod) Cream, 2.5% and to establish the superiority of the efficacy of these two products over the vehicle cream in the treatment of actinic keratoses (AK).			
Study Design	Multicenter, randomized, double-blind, vehicle-controlled, parallel group comparison.			
Treatment Groups	After enrollment in the study, each subject will be randomized to treatment with Zyclara, generic imiquimod, or vehicle control.			
Duration of Treatment	Two 2-week treatment cycles separated by a 2-week no-treatment period and an 8-week follow-up period.			
Duration of Study	Approximately 14 weeks (not including up to 30-day screening period).			
Study Population	Male or female subjects, age 18 years or older with actinic keratoses on the face or balding scalp.			
Total Number of Subjects	Approximately 435 subjects will be enrolled.			
Number of Sites	Approximately 25 sites will participate in the study.			
Inclusion Criteria	To enter the study, a subject must meet the following criteria:			

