Study Endpoints	Efficacy Endpoint(s) Complete clearance rate (treatment success), defined as the proportion of subjects in each treatment group at Visit 7 (Week 14/ End of Study Visit) in the per-protocol (PP) population with a count of zero AK lesions in the treatment area. All AKs (baseline and new lesions) independent of size within the treatment area will be included in the efficacy lesion count for each visit.
	Safety Endpoint(s) Dosing Compliance: Measures of test article compliance will include the total number of applications recorded in the case report forms (CRFs) and verified from the data in the subject diaries. Compliant subjects are defined as those who apply at least 75% and no more than 125% of the test article applications and no other evidence of material dosing noncompliance.
	Adverse Events: Assessment of the severity and frequency of adverse events including LSRs in the three treatment groups.
Sample Size Calculations	Bioequivalence was concluded if the 90% continuity-corrected confidence interval on the difference in active treatment complete clearance rates was between -0.20 and +0.20 in the per protocol (PP) population, and each active treatment was found to be statistically superior to the vehicle by independent continuity-corrected Z-tests in the intent-to-treat (ITT) population. A total of 435 ITT subjects for demonstrating superiority of each active treatment over the vehicle treatment.
Statistical Methods	All statistical processing will be performed using SAS® unless otherwise stated.

Sponsor Name: Actavis, LLC Protocol: 094-3153-301, v1.0

Efficacy summaries and analyses will be carried out in the ITT and PP populations. All summaries of safety will be carried out in the Safety population. Last-observation-carried-forward (LOCF) will be used to impute missing values for efficacy variables in the ITT population.

Demographic and baseline characteristics will be summarized by treatment group for the ITT and PP populations. The size of the treatment area (in centimeters) at baseline will be determined from an estimate of the % BSA treated. BSA will be determined from the subject's height and weight using the Mosteller formula. Frequency counts and percentages will be reported for categorical data. Sample size, mean, standard deviation, and minimum and maximum will be reported for the continuous variables.

Efficacy Analyses:

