5. STUDY POPULATION

Approximately 435 adult male and female subjects with 5 (five) to 20 AKs that are at least 4 mm in diameter on the full face or balding scalp who meet the entry criteria will be enrolled into the treatment phase of the study.

Sponsor Name: Actavis, LLC Protocol: 094-3153-301, v1.0

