5.1.3 Subject Withdrawal Criteria

Procedures for handling subjects who are discontinued from the study are described in **Section 13.2**. Subjects who are discontinued will not be replaced.

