17.3 Statistical Methods

All statistical processing will be performed using SAS® unless otherwise stated. The Safety population will include all randomized subjects who received the test article.

The Intent-to-Treat (ITT) population will include all randomized subjects who applied at least one dose of test article and returned for at least one post-baseline evaluation visit.

Subjects will be included in the PP efficacy analyses if they met all the inclusion/exclusion criteria, were compliant with the assigned test articles (applied at least 75% and no more than 125% of the test article applications and no other evidence of material dosing noncompliance), completed the evaluation at Week 14 within the designated visit window (± 4 days) with no protocol violations that would affect treatment evaluation. Subjects who are discontinued from the study due to lack of treatment effect or due to worsening condition that requires alternate or supplemental therapy for the treatment of AK should be included in the PP population as treatment failures (non-responders). Subjects discontinued prematurely for other reasons should be excluded from the PP population, but included in the ITT population using the Last Observation Carried Forward (LOCF) to impute missing values for efficacy variables.

Efficacy summaries and analyses will be carried out in the ITT and PP populations. All summaries of safety will be carried out in the safety population.

Demographic and baseline characteristics will be summarized by treatment group for the ITT and PP populations. The size of the treatment area (in centimeters) at baseline will be determined from an estimate of the % BSA treated. BSA will be determined from the subject's height and weight using the Mosteller formula. Frequency counts and percentages will be reported for categorical data. Sample size, mean, standard deviation, and minimum and maximum will be reported for the continuous variables.

Sponsor Name: Actavis, LLC Protocol: 094-3153-301, v1.0

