7 DATA SETS ANALYZED

The Safety population will include all randomized subjects who received the test article. Subjects who were randomized and applied at least one dose oftest article and returned for at least one post-Baseline evaluation will be included in the intent-to-treat (ITT) population. Subjects who complete the two, 2-week cycles of treatment and all of the Visit 7 follow-up evaluations at Week 14 will be considered to have completed the study.

Efficacy summaries and analyses will be carried out in the ITT and PP populations. All summaries of safety will be carried out in the Safety population.

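### The superiority sample size is given as 435 ITT subjects, the same figure as planned enrolment, with no visible allowance for early loss

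*Protocol*

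**What the plan says.** **Size for superiority.** The Protocol Synopsis (Sample Size Calculations) reads "A total of 435 ITT subjects for demonstrating superiority of each active treatment over the vehicle treatment". Section 17.1 gives the same figure, "total of 435 ITT subjects", with text removed around it, and then the purpose, "for demonstrating superiority of each active treatment over the vehicle treatment".

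**Size enrolled.** The Synopsis (Total Number of Subjects) says "Approximately 435 subjects will be enrolled". Protocol Section 4 and SAP Section 4 agree. Protocol Section 5 says that these subjects "will be enrolled into the treatment phase of the study", so the figure is not a screening count.

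**Replacement.** Protocol 5.1.3: "Subjects who are discontinued will not be replaced". Section 13.2 repeats the rule for premature withdrawals.

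**ITT definition.** Protocol 17.3 limits ITT to randomised subjects "who applied at least one dose of test article and returned for at least one post-baseline evaluation visit". SAP Section 7 has the same restriction: subjects who were randomised, dosed and "returned for at least one post-Baseline evaluation will be included in the intent-to-treat (ITT) population".

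**Role of ITT.** Protocol 17.3.1 and SAP 8.7.1 make ITT the primary population for the two comparisons with vehicle. Both must succeed before therapeutic equivalence is concluded.

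**The concern.** One number labels both a whole set and a subset of it. Anyone who never doses, or who doses and never returns, is enrolled but not in ITT, and nobody takes that place. A size calculation stated in ITT subjects normally leads to a somewhat larger enrolment target, or else the 435 is labelled as randomised and a smaller ITT number is given. Neither is visible here.

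At stake is the reading of a required part of the equivalence claim. If the superiority power was worked out for 435 ITT subjects, it is the power at zero early loss, and the documents should say so or give the figure at a realistic ITT size.

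**Working it through.** **Inputs from the documents.** ITT total for superiority 435 (Synopsis, 17.1). Enrolment about 435 (Synopsis, Sections 4 and 5). Replacement none (5.1.3, 13.2). Test: two-sided continuity-corrected Z-test, p<0.05 (17.3.1).

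**Assumed, because the documents give no readable value.** Early-loss rate, allocation ratio and clearance rates.

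**1. The plan's own figure.** The 435 cannot be reproduced without the rates, power and allocation. Under assumed 2:2:1 allocation, 5% vehicle clearance and 90% power with continuity correction, an active rate of 20% needs 87 vehicle subjects, 5 × 87 = 435 in total. An active rate of 30% needs 42, or 5 × 42 = 210. So 435 could be a bare minimum or could carry ample spare power. Neither set of inputs can be attributed to the sponsor.

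**2. ITT size from 435 enrolled.** ITT = 435 × (1 − loss).
- 1%: 435 × 0.99 = 430.65, about 431
- 3%: 435 × 0.97 = 421.95, about 422
- 5%: 435 × 0.95 = 413.25, about 413

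**3. Enrolment that would deliver 435 ITT.** Enrolment = 435 / (1 − loss), rounded up.
- 1%: 435 / 0.99 = 439.4, so 440
- 2%: 435 / 0.98 = 443.9, so 444
- 3%: 435 / 0.97 = 448.5, so 449
- 5%: 435 / 0.95 = 457.9, so 458

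**4. Effect on power per comparison (illustration only).** Superiority is declared when (pA − pV − c) / SE ≥ 1.96, where pA and pV are the observed rates, c = ½(1/nA + 1/nV), SE = √[p(1 − p)(1/nA + 1/nV)] and p is the pooled rate. Power is the exact binomial probability of all outcomes that meet this. Arm sizes (active v vehicle) are 174 v 87 for 2:2:1 and 145 v 145 for 1:1:1; at 5% loss, 165 v 83 and 138 v 138.

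| Allocation, active v vehicle | (a) No loss | (b) 5% lost, rates unchanged | (c) 5% lost, all would have been failures | (d) 5% kept and counted as failures |
|---|---|---|---|---|
| 2:2:1, 20% v 6% | 85.6% | 82.7% | 85.3% | 83.0% |
| 2:2:1, 25% v 10% | 81.4% | 78.3% | 81.3% | 78.5% |
| 2:2:1, 25% v 12% | 65.7% | 62.1% | 65.6% | 62.5% |
| 1:1:1, 25% v 10% | 90.7% | 88.9% | 90.9% | 88.6% |

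In (c) the listed rates apply to everyone dosed, so deleting failures raises both arms' rates by a factor 1/0.95. In (d) the listed rates apply to those who return, so both arms' rates fall by a factor 0.95 while all 435 stay in.

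For 30% v 6% the difference between (a) and (b) is a fraction of a point under either allocation. A wider grid by normal approximation (1:1:1 to 4:4:1, vehicle 5% or 10%, active 15% to 30%) gives a largest 5%-loss cost of 66.96 − 63.37 = 3.59 points, at 4:4:1 with 20% v 5%.

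**The case against.** **The statements are not strictly incompatible.** A reader might infer that they cannot all be true. Enrolment is always given as approximate, and step 3 shows that 440 or 444 enrolled would cover a loss of 1% or 2%; either is fairly described as about 435. Zero early loss would also satisfy everything. This stands: what can be said is that no allowance is visible. It does not explain why the same number carries both labels.

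**The key sentence is incomplete.** Text is missing on both sides of the 435 in 17.1, and SAP 8.9 is cut to the end of a sentence. A reader might infer that the stated power is overstated or that the trial is too small. The documents do not support that, because the power cannot be read and 435 may include a margin. The mismatch itself remains, since both totals and the ITT definition are readable and no hidden text can make ITT larger than the enrolled set.

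**The group lost is small.** Anyone who withdraws after one post-baseline visit stays in ITT by last observation carried forward (17.3). The first return visit is at Day 15, and 13.2 asks sites to make every effort to bring withdrawing subjects back. This stands and limits the size of the point.

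**Bias and redefinition.** A reader might also infer that deleting early dropouts inflates the active-arm clearance rate and that a wider ITT definition would restore power. Inflation requires the deleted subjects to be failures, and the rule applies to vehicle as well. On that assumption, column (c) shows almost no change in power, so the inflation and the power loss in (b) cannot both be claimed in full. Column (d) shows that keeping these subjects as failures leaves power essentially where (b) has it. Treating them as failures also relies on carrying the baseline count forward, which 17.3 does not spell out; the body of SAP 8.5 is not available. The ITT definition is explicit, and the same in both documents.

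**Conclusion.** The point holds as an inconsistency in a stated size. Protocol 17.1 and the Synopsis count 435 in ITT, the enrolment statements count about 435 in total, and the no-replacement rule and ITT definition make the first a subset of the second without a visible allowance. From 435 enrolled, one subject who never doses or never returns gives 434; the assumed losses of 1% to 5% give about 431 to 413.

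The consequence is modest. Under the assumed rates and allocations, a 5% loss costs between a fraction of a point and about 3.6 points of power per comparison, and the loss rate is itself an assumption. The finding does not show that the trial is underpowered, that its ITT definition is wrong, or that the ITT clearance rates are biased. The per-protocol size for equivalence is not readable and is not part of this point.

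**What to change.** In the Synopsis, Protocol 17.1 and SAP 8.9:
- label 435 as the number randomised;
- state the expected ITT number after a stated early-loss rate;
- restate the superiority power at that number.

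The SAP 8.4 dropout listing, which records whether a subject was replaced, should be brought into line with the no-replacement rule in Protocol 5.1.3 and 13.2.

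The cost is wording and a stated size or power that is slightly less favourable. No extra patients are needed.

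The ITT definition need not change for reasons of size or power. At most, add a sensitivity analysis of the superiority comparisons in all randomised subjects who applied at least one dose, counting those with no post-baseline AK count as not cleared. It costs one additional table.

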17.2 Endpoints

17.2.1 Efficacy Endpoint(s)

Complete clearance rate (treatment success), defined as the proportion of subjects in each treatment group at Visit 7 (Week 14/ End of Study) in the per-protocol (PP) population with a count of zero AK lesions in the treatment area. All AKs (baseline and new lesions) independent of size within the treatment area will be included in the efficacy lesion count for each visit.

Sponsor Name: Actavis, LLC Protocol: 094-3153-301, v1.0

17.2.2 Safety Endpoint(s)

17.2.2.1 Dosing Compliance

Measures of test article compliance will include the total number of applications as determined from the data recorded in the subject diaries.

17.2.2.2 Adverse Events

Safety endpoints will also include assessment of the severity and frequency of adverse events including local skin reactions (LSRs) in the three treatment groups.

17.3 Statistical Methods

All statistical processing will be performed using SAS® unless otherwise stated. The Safety population will include all randomized subjects who received the test article.

The Intent-to-Treat (ITT) population will include all randomized subjects who applied at least one dose of test article and returned for at least one post-baseline evaluation visit.

Subjects will be included in the PP efficacy analyses if they met all the inclusion/exclusion criteria, were compliant with the assigned test articles (applied at least 75% and no more than 125% of the test article applications and no other evidence of material dosing noncompliance), completed the evaluation at Week 14 within the designated visit window (± 4 days) with no protocol violations that would affect treatment evaluation. Subjects who are discontinued from the study due to lack of treatment effect or due to worsening condition that requires alternate or supplemental therapy for the treatment of AK should be included in the PP population as treatment failures (non-responders). Subjects discontinued prematurely for other reasons should be excluded from the PP population, but included in the ITT population using the Last Observation Carried Forward (LOCF) to impute missing values for efficacy variables.

Efficacy summaries and analyses will be carried out in the ITT and PP populations. All summaries of safety will be carried out in the safety population.

Demographic and baseline characteristics will be summarized by treatment group for the ITT and PP populations. The size of the treatment area (in centimeters) at baseline will be determined from an estimate of the % BSA treated. BSA will be determined from the subject's height and weight using the Mosteller formula. Frequency counts and percentages will be reported for categorical data. Sample size, mean, standard deviation, and minimum and maximum will be reported for the continuous variables.

Sponsor Name: Actavis, LLC Protocol: 094-3153-301, v1.0

